## 9.6 DATA QUALITY ASSURANCE

## 9.6.1 Monitoring

The sponsor had ethical, legal, and scientific obligations to follow the study in a detailed and orderly manner in accordance with established research principles, the ICH GCP Guideline, FDA regulations and applicable regulatory requirements and local laws. As part of a concerted effort to fulfill these obligations (i.e., maintain current personal knowledge of the progress of the study), an independent group of the sponsor's monitors contracted from Washington University School of Medicine (WUSM), separate from the clinical site staff at WUSM, could visit the site during the study, as well as communicate frequently via telephone and written communications.

## 9.6.2 Auditing

The OAPI Quality Management Unit (or representative) could conduct study site audits. Audits would include, but were not be limited to, drug supply, presence of required documents, the informed consent process, and comparison of CRFs with source documents. The sponsor agreed to participate with audits.

Regulatory authorities could inspect the sites during or after the study. The sponsor agreed to cooperate with such inspections and to contact the sponsor and OAPI immediately if such an inspection occurs.

#### 9.6.3 Data Collection

The study was expected to start in the spring of 2016 and be completed on or about 01 December 2018. Data collection began when the first subject signed the ICF, on 08 June 2016 and would have been completed on the date at which the last subject's data has been entered into the database and no data queries are outstanding, approximately 01 November 2018.

## 9.7 STATISTICAL METHODS

The plan analyses are described below. No actual formal statistical analyses were performed.

#### 9.7.1 Statistical and Analytical Plans

#### 9.7.1.1 Primary Endpoint(s)

The primary efficacy endpoint was:

 Comparison of rates of psychiatric re hospitalization for symptoms associated with schizophrenia after receiving aripiprazole once monthly for 30, 90, and 180 days following hospital discharge for acute psychiatric stabilization, compared with retrospective 30-, 90-, and 180-day hospitalization rates, respectively, in subjects previously treated with oral antipsychotic medication.

Final; 26 Feb 2018 Page 52 of 80

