#### 7.4 STUDY RATIONALE

Non-adherence to antipsychotic medication is a well-established risk factor for symptomatic relapse. LAI antipsychotics can improve treatment adherence, but at the time of this study there were, to our knowledge, no study on the effect of LAI antipsychotics on the policy- and cost-relevant endpoint of 30-day hospital readmission rates.

The primary hypothesis was that treatment with aripiprazole once monthly would result in lower hospitalization rates for psychiatric symptom recurrence than patients experienced prior to treatment with aripiprazole once monthly.

The secondary hypotheses were that treatment with aripiprazole once monthly would result in fewer unscheduled psychiatric emergency department (ED) visits, ED visits associated with psychiatric hospitalization, and fewer total psychiatric hospitalization days than patients experienced prior to treatment with aripiprazole once monthly. In addition, we hypothesize that clinical functioning, measured by CGI-S and CGI-I scores, and change from baseline in measures of cardiometabolic risk (CMR) such as weight, body mass index (BMI), fasting glucose, and glycosylated hemoglobin (HbA1c) would improve from baseline in patients treated with aripiprazole once monthly that were previously treated with oral antipsychotics.

The study design, following well-characterized subjects for 180 days after starting aripiprazole once monthly treatment, and retrospectively reviewing data regarding prior hospitalizations, psychiatric ED visits, and prior total psychiatric hospitalization days, will allow the proposed hypotheses to be tested.

Final; 26 Feb 2018 Page 20 of 80

ClinicalTrials.gov Identifier: NCT02717130

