#### 8 STUDY OBJECTIVES

#### 8.1 PRIMARY OBJECTIVE(S)

The primary objective of the study was:

• To evaluate the effect of aripiprazole once monthly on 30-, 90-, and 180-day psychiatric re-hospitalization rates following discharge due to symptoms associated with schizophrenia, compared with prior 30-, 90-, and 180-day psychiatric hospitalization rates in subjects previously treated with oral antipsychotic medication.

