#### **DOCUMENTATION OF PREVIOUS HOSPITALIZATIONS**

Data regarding psychiatric and non-psychiatric hospitalizations and medical interventions occurring within the 6 months prior to the date of the signing the ICF were obtained by searching MO HealthNet (Medicaid) and the DMH database or confirmed through all available medical records and reliable data from caregivers.

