## 9.7.1.9 Efficacy Analyses

The primary objective of the study was to evaluate the effect of aripiprazole once monthly on 30-, 90-, and 180-day psychiatric re-hospitalization rates following discharge due to symptoms associated with schizophrenia, compared with retrospective 30-, 90-, and 180-day psychiatric hospitalization rates in subjects previously treated with oral antipsychotic medication.

Because all primary and secondary outcome measures described in the specific aims were continuous and a reflection of a single design configuration involving longitudinal measures, in some cases including retrospective as well as prospective time points, the basic structure of the data analytic strategies was the same for all objectives.

The primary and secondary outcomes were to be analyzed using repeated measures analysis of covariance (ANCOVA) models. For example, in the three primary outcome models, testing for a main effect of time on 30-, 90-, or 180-day pre-hospitalization (i.e., oral antipsychotic) versus 30-, 90-, or 180-day post-hospitalization (i.e., aripiprazole once monthly) rates, respectively. Covariates would have included psychiatric symptoms severity at baseline, measured by CGI-S scores.

Some secondary outcome measures such as BMI, fasting lipid parameters, and glucose that were measured at time points post-hospitalization only (i.e., at baseline, 30-, 90-, and 180-days) were to be evaluated using mixed model repeated measures analysis of variance to determine whether there are changes over time. Other covariates could include race, gender, age, family history of diabetes, and BMI.

Only one primary specific objective was defined, with three time-point comparisons (i.e., 30, 90, and 180 days) with the primary comparison being hospitalization rate for the period of 30 days pre-hospitalization (i.e., at least one, based on the index hospitalization) to 30 days post-hospitalization both because of the importance of that objective and to minimize multiple comparisons concerns. Because of the multiple comparisons issue, p-values associated with the secondary and exploratory analyses performed were to be interpreted cautiously as hypothesis-generating rather than as hypothesis-confirming.

Final; 26 Feb 2018 Page 56 of 80

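### The primary endpoint in 9.7.1.1 restricts post-switch admissions more narrowly than pre-switch ones and disagrees with 8.1 and 9.7.1.9; any resulting bias favours the drug, but it cannot be sized

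*Combined protocol and SAP*

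**What the plan says.** Section 9.7.1.1 states the primary endpoint as "Comparison of rates of psychiatric re hospitalization for symptoms associated with schizophrenia after receiving aripiprazole once monthly for 30, 90, and 180 days following hospital" […]. The same sentence gives the pre-switch side: "compared with retrospective 30-, 90-, and 180-day hospitalization rates, respectively, in subjects previously treated with oral antipsychotic medication". The first half carries two restrictions (psychiatric, and for schizophrenia symptoms). The second half carries neither.

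The primary objective in 8.1 concerns "psychiatric re-hospitalization rates following discharge due to symptoms associated with schizophrenia", and its comparator is worded "compared with prior 30-, 90-, and 180-day psychiatric hospitalization rates in subjects previously treated with oral antipsychotic medication". Section 9.7.1.9 restates it with the comparator "compared with retrospective 30-, 90-, and 180-day psychiatric hospitalization rates in subjects previously treated with oral antipsychotic medication". In both places the pre-switch side is limited to psychiatric admissions, and the schizophrenia phrase is most naturally read as describing the index discharge, not the readmission. The hypothesis in 7.4 is "lower hospitalization rates for psychiatric symptom recurrence than patients experienced prior to treatment with aripiprazole once monthly", which applies one notion of event to both periods.

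On data capture, the part of 9.5.1.3 on previous hospitalizations says: "Data regarding psychiatric and non-psychiatric hospitalizations and medical interventions occurring within the 6 months prior to the date of the signing the ICF were obtained". After the switch, 9.1.4.2 has every episode of care, psychiatric or not, entered in the source documents. No section gives a definition of a qualifying admission, a diagnosis code list or an adjudication rule that applies to both windows.

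**The concern.** In a within-subject comparison of two periods, the event has to mean the same thing in each. If a stay must pass an extra test to count after the switch but not before it, part of any fall in the rate comes from the definition. A programmer working from 9.7.1.1 would build a different post-switch numerator from one working from 8.1 or 9.7.1.9, and nothing in the plan says which governs. The sentence covers the primary endpoint at 30, 90 and 180 days, so all three comparisons inherit the ambiguity.

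**Working it through.** The plan offers no figure of its own on this point to reproduce, so the check is a comparison of wordings followed by a short algebraic argument.

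**Scope of a counted admission, by section**

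| Section | Before the switch | After the switch |
|---|---|---|
| 9.7.1.1 | any hospitalization, no qualifier | psychiatric, for schizophrenia symptoms |
| 8.1 and 9.7.1.9 | psychiatric | psychiatric |
| Synopsis (Study Design) and 9.1 | psychiatric | psychiatric |
| 7.4 | psychiatric symptom recurrence | psychiatric symptom recurrence |
| Synopsis (Statistical Methods) and 9.7.2 | no qualifier | no qualifier |

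Only 9.7.1.1 puts different scopes on the two sides.

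**Direction of the effect**

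In a given window, let H be the proportion of subjects with any admission, A the proportion with a psychiatric admission, and S the proportion with a psychiatric admission attributed to schizophrenia. Each group is contained in the one before it, so S ≤ A ≤ H.

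The like-for-like difference is A(pre) − A(post). The difference under 9.7.1.1 read literally is

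H(pre) − S(post) = [A(pre) − A(post)] + [H(pre) − A(pre)] + [A(post) − S(post)].

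The last two brackets are zero or positive. Neither depends on comparing the drug with prior treatment, and both push the difference towards a reduction.

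- *Second bracket (non-psychiatric stays before the switch).* It is zero if the pre-switch side is psychiatric, as 8.1 and 9.7.1.9 say.
- *Third bracket (psychiatric stays after the switch not attributed to schizophrenia).* It remains under that reading. It is zero if every post-switch psychiatric stay is so attributed, and positive otherwise.

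**Effect of the index stay**

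Section 9.7.1.9 counts the index hospitalization in the 30-day pre-switch window, and 9.7.2 states that 100% of subjects therefore have at least one pre-switch hospitalization. Inclusion criterion 4 makes that stay an admission with acute psychotic symptoms, so it qualifies under every wording. Hence S(pre) = A(pre) = H(pre) = 100%, and the second bracket is 100% − 100% = 0 on the proportion scale. Harmonising the pre-switch wording would not move that proportion. Scope can still alter the post-switch proportion. It can also alter the number of stays per subject, which 9.7.1.10 compares, because pre-switch stays beyond the index admission depend on it.

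**Size**

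Sizing the third bracket requires the share of subjects whose only post-switch psychiatric admissions fall outside the schizophrenia qualifier. The documents give no such share. The logical bounds run from zero to the whole post-switch rate, which is uninformative.

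**The case against.** The strongest reply is that 9.7.1.1 is shorthand. The secondary endpoints in 9.7.1.2 show the same habit: unscheduled psychiatric emergency department visits become plain unscheduled visits on second mention, and nobody would read that as a different event. The summary of Amendment 2.0 (9.8.1.2) calls the rewording of the primary endpoint administrative, for consistency with other sections. Section 9.7.1.9, which specifies the analysis, is symmetric. All of this stands, and it makes a deliberate difference in scope unlikely. It does not settle which common scope was meant. If both qualifiers carry over, the endpoint is schizophrenia-attributed in both windows; if 8.1 and 9.7.1.9 govern, it is all psychiatric admissions.

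A reader might infer several stronger points that the documents do not support:

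- *Pre-switch counting is unrestricted and takes in medical stays.* The Synopsis, 8.1, 9.1 and 9.7.1.9 all limit it to psychiatric admissions. Non-psychiatric episodes are recorded in both periods, and recording them does not mean counting them.
- *The post-switch rate is lower by definition.* It is equal or lower.
- *Open-label site staff would judge the cause of readmission.* The study is unblinded (9.4.4), but no section says who classifies admissions.
- *Readmissions for suicidality, depression or substance use would be excluded.* No section says so. The exclusions in 9.3.2 for significant suicide risk, recent substance use disorder and psychosis explained by other diagnoses would also make some such events less common.

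**Conclusion.** The inconsistency is real and should be fixed, but it is not a demonstrated bias. Section 9.7.1.1 conflicts with 8.1 and 9.7.1.9 on which admissions count. The likely residual mismatch, taking the pre-switch restriction from those two sections, is all psychiatric admissions before against schizophrenia-attributed psychiatric admissions after. Any effect runs towards the drug; its size may be zero and cannot be estimated from the documents.

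It is tempting to assume an out-of-scope share, apply it to the 30% planning rate in 9.7.2, and set the result against the planned fall of 30% − 15% = 15 points. That does not hold up. The share would be invented, a share of admissions is not a share of subjects (someone with another in-scope stay still counts), and with the index stay counted the pre-switch proportion is 100%, not 30%.

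The study ended early and Section 9.7 states that no formal analysis was done, so the point concerns the plan as written and no reported finding changes.

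**What to change.** Reword 9.7.1.1 to agree with 8.1 and 9.7.1.9: one event, any inpatient psychiatric admission, defined by the same facility types and the same diagnosis rule in the pre-switch and post-switch windows. Report schizophrenia-attributed admissions only as a sensitivity analysis, with the same classification rule in both windows.

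The text change is one sentence plus a short event definition. There are two costs. The post-switch rate may look slightly less favourable. A common code rule may also need the Medicaid and Department of Mental Health search, which the plan specifies only for the 6 months before consent, to be repeated for the post-switch period, because post-switch episodes are otherwise taken from source documents.

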## 9.7.1.2 Secondary Endpoint(s)

The secondary endpoints were:

## Efficacy:

- Comparison of:
  - o 30-, 90-, and 180-day rates of unscheduled psychiatric ED visits compared with prior 30-, 90-, and 180-day unscheduled visits
  - Psychiatric ED visits plus hospitalizations compared with prior 30-, 90-, and 180-day psychiatric visits plus hospitalizations
  - Total psychiatric hospitalization days over the 30-, 90- and 180-day study period compared with the total psychiatric hospitalization days over the prior 30-, 90- and 180-day period
  - o Change from baseline in CGI-I, based on the initial CGI-S, and CGI-I scores at 30-, 90-, and 180-days
- Changes from baseline on the following indicators for CMR after receiving aripiprazole once monthly:
  - Weight and BMI
  - o Fasting glucose concentrations, HbA1c concentrations, and fasting lipids concentrations (i.e., fasting triglyceride, total cholesterol, HDL, and LDL)

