# 9.3.1 Inclusion Criteria

Subjects must have met all of the following criteria to be included in this study:

- 1. Were able to provide written informed consent.
- 2. Were male and female subjects 18 to 65 years of age, inclusive, at time of informed consent

Final; 26 Feb 2018 Page 30 of 80

- 3. Had a current and confirmed diagnosis of schizophrenia as defined by DSM-5 criteria and a history of the illness for at least 6 months prior to screening from a reliable source (e.g., subject, family member, friend, caregiver, healthcare provider, or medical records)
- 4. Present at one of the selected inpatient units with acute psychotic symptoms for hospitalization at study entry
- 5. Had a clinically indicated need for a change in current antipsychotic therapy
- 6. Were on Medicaid with searchable claims data or were Medicaid-eligible
- 7. Had at least one inpatient psychiatric hospitalization or psychiatric ED visit within the 6 months prior to screening as confirmed through Medicaid or all available medical records and reliable data from caregivers
- 8. Had been previously prescribed oral antipsychotic treatment for at least a substantial portion of the 6 consecutive months prior to screening, with estimated duration of prescribed treatment within the 6 months prior to screening as determined by Principal Investigator discretion and confirmed through Medicaid or all available medical records and reliable data from caregivers
- 9. Had a history of response to antipsychotic treatment, with no history of clozapine treatment
- 10. Were able to understand the nature of the study and follow protocol requirements, including the prescribed dosage regimens, tablet ingestion, aripiprazole once monthly injection, and discontinuation of prohibited concomitant medications
- 11. Were able to read and understand the written word with a passing score of 4 to 6 (i.e., equivalent to seventh to eighth grade reading level for REALM-SF literacy assessment) in order to complete subject-reported outcomes measures
- 12. Were willing to accept a monthly injection
- 13. Were male and female subjects who were surgically sterile (i.e., have undergone orchiectomy or hysterectomy, respectively); female subjects who were postmenopausal for at least 12 consecutive months; or male and female subjects who agreed to use an approved form of birth control during study participation

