d: Previous medications taken within 7 days prior to starting study drug and all central nervous system-active compounds taken within 30 days preceding the first dose of study drug were recorded. All antipsychotic medications used within 6 months of screening were recorded.

e: A urine pregnancy test was performed for women of childbearing potential only at screening, Visit 10, and at the Follow-up visit; subsequent testing was done as is clinically indicated. If a subject or investigator suspected that the subject may be pregnant, a serum pregnancy test would then be performed.

**Table 3:** Schedule of Assessments

Visit				2	3	4	5	6	7	8 q
Study Period	Screening/ Assessment	Phase A (Oral Tolerability Phase a )			Pha	nse B (Trea	tment Ph	ase)		
Day	Variable	-3 to -1	Baseline Day 1 b,g	15 g	30	60	90	120	150	180
Week				2 e	4	8	12	16	20	24
Procedure										

- f: Data regarding psychiatric and non-psychiatric hospitalizations and medical interventions occurring within the 6 months prior to the date of the signing the ICF were obtained by searching MO HealthNet (Medicaid) and MO Department of Mental Health (DMH) data via collaboration with the Missouri Institute of Mental Health (MIMH); availability of Medicaid data and documentation of at least one inpatient hospitalization or ED visit within the previous 6 months was required for eligibility.
- g: For subjects who were psychiatrically stabilized and discharged prior to the completion of the required 14-day course of oral aripiprazole, a pre-discharge assignment was given to a CSW or SC. The CSW/SC maintained regular contact with the subject until the Week 2 visit. Following the Week 2 visit, subjects had contact with their assigned CSW/SC based on routine clinical care.
- h: At all outpatient visits, scheduled or unscheduled.
- i: Vital signs were recorded daily while hospitalized.
- j: BMI was calculated as: mass (kg)/height (m2).
- k: Subjects should have been fasting for a minimum of 10 hours prior to blood draws for all laboratory assessments. Every effort was made to obtain the clinical laboratory samples at the same time of day at each visit. All laboratory testing was performed at local laboratories at the clinical sites.

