## 9.7.2 Determination of Sample Size

The primary endpoints of this study were comparisons of the rate of hospitalization for specified pre-hospitalization (i.e., pre-aripiprazole once monthly) timeframes (i.e., 30-, 90-, and 180-days) to corresponding post-hospitalization timeframes. Based on published results of other studies, it was generally reasonable to assume 30% of subjects would be hospitalized pre-medication switch and 15% would be hospitalized post-switch to aripiprazole once monthly. In this study, 100% of the pre-aripiprazole once monthly subjects would have had at least one hospitalization (i.e., index inpatient hospitalization at least). The estimated sample size of 90 completed subjects would have provided approximately 80% power (alpha = 0.05 two-sided) to detect a clinically relevant difference between pre-switch and post-switch hospitalization rates. The recent Otsuka Mirror study had 121 completers with only a 28% pre-switch hospitalization rate, compared to the present design with a 100% pre-switch hospitalization rate, with highly significant reductions in total psychiatric hospitalization rates in the Mirror study. A medium effect size = 0.5 with a sample size of N = 90 provided approximately 80% power to detect significance at the 5% level (two-tailed test).

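### Inclusion 7 selects on the same psychiatric events that the 180-day ED-plus-hospitalization endpoint counts as its pre-switch value, so the pre/post test can show a reduction with an inactive drug

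*Combined protocol and SAP*

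**What the plan says.** - **Endpoint (9.7.1.2, Efficacy):** "Psychiatric ED visits plus hospitalizations compared with prior 30-, 90-, and 180-day psychiatric visits plus hospitalizations".
- **Entry rule (9.3.1, item 7):** "Had at least one inpatient psychiatric hospitalization or psychiatric ED visit within the 6 months prior to screening". Item 4 separately requires that subjects be "Present at one of the selected inpatient units with acute psychotic symptoms for hospitalization at study entry".
- **Source of prior events:** the 6-month Medicaid and Department of Mental Health search, or medical records and caregiver data (9.1.2, 9.5.1.3). Table 3, footnote f, says that "availability of Medicaid data and documentation of at least one inpatient hospitalization or ED visit within the previous 6 months was required for eligibility". Section 9.1.2 joins the same two conditions with *or*.
- **Analysis (9.7.1.9):** "The primary and secondary outcomes were to be analyzed using repeated measures analysis of covariance (ANCOVA) models". For the primary models this means "testing for a main effect of time on 30-, 90-, or 180-day pre-hospitalization (i.e., oral antipsychotic) versus" the matching post-hospitalization rate. The covariate named for these models is baseline CGI-S.
- **Index admission:** for the 30-day primary comparison, 9.7.1.9 describes the pre-period count as "at least one, based on the index hospitalization". Section 9.7.2 adds: "In this study, 100% of the pre-aripiprazole once monthly subjects would have had at least one hospitalization". No text removes the index admission, or the event that met inclusion 7, from any pre-period count.
- **Control:** there is none. The study is single-arm (9.4.3), and 9.2 calls the pre/post comparison relatively equivalent without discussing regression to the mean.

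**The concern.** The selection variable and the pre-period outcome are the same kind of event in almost the same window. Subjects enter because they had such an event; afterwards they are free to have none. The pre-period mean is therefore raised by selection, while the post-period mean reflects the subject's underlying rate. A test of the time effect reads the difference as change. CGI-S at baseline does not undo selection on the outcome, and no control arm shows what would have happened without the switch.

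At stake is the secondary hypothesis in 7.4 on ED visits and hospitalization, which could appear supported at 180 days by the entry rule alone. There is also a trap in a partial repair: someone who removes only the index admission may think this endpoint is clean when it is not.

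**Working it through.** **1. The plan's own figure.** None is given for this endpoint. The nearest is about 80% power with 90 completers (9.7.2), for hospitalization falling from 30% to 15%. That does not reproduce: two independent groups of 90 give 67.6%, and 90 uncorrelated pairs (McNemar) give 66.5%. This is a separate matter. I take from 9.7.2 only N = 90, the two-sided 5% level and the 30% rate. The plan attaches no time window to that 30% and applies it to hospitalization, so using it for the 180-day composite is my assumption.

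**2. Events and windows side by side.**

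| | Inclusion 7 | Pre-switch composite | Post-switch composite |
|---|---|---|---|
| Events | psychiatric admission or ED visit | psychiatric ED visits plus hospitalizations | same |
| Window | 6 months before screening | prior 180 days | 180 days after |
| Minimum | 1 by rule | 1 by selection | 0 |

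Six months is 181-184 days, so the mismatch is trivial. Inclusion 7 guarantees the floor only for the 180-day window, not for 30 or 90 days.

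**3. Expected counts, no drug effect, index admission removed, a separate qualifying event for everyone.** Let p be the share of the source population with at least one event in 180 days.

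- *Same rate L for all:* E[pre | pre ≥ 1] = L/(1 − exp(−L)), which always exceeds E[post] = L. At p = 0.30, L = −ln(0.70) = 0.357. The pre mean is 0.357/0.30 = 1.19 and the post mean 0.357, a ratio of 0.30.
- *Rates varying as a gamma with shape k and scale θ:* (1 + θ)^(−k) = 1 − p and m = kθ. The pre mean is m/p and the post mean is (m/p)[1 − (1 + θ)^(−(k+1))]. At p = 0.30, k = 0.5: 1 + θ = 0.70^(−2) = 2.041 and m = 0.520. The pre mean is 0.520/0.30 = 1.73 and the post mean 1.73 × (1 − 0.343) = 1.14.

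**4. How often this is significant.** Pre and post counts were drawn from the same subject rate, subjects were kept only if pre ≥ 1, and a paired two-sided 5% t-test was applied to 90 subjects. The paired t-test stands in for a two-level time effect. The table shows the percentage of trials with a false reduction (nominal 2.5% in that direction); ranges within a cell are the spread of repeat runs.

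| Source rate p | k = 0.3 | k = 0.5 | k = 1 | no variation |
|---|---|---|---|---|
| 30% | 67-71 | 96-97 | 100 | 100 |
| 50% | 12-14 | 35-36 | 79-81 | 100 |
| 70% | 4 | between | between | 91-93 |

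The 4% corner needs a mean of 0.3 × (0.3^(−1/0.3) − 1) ≈ 16 events per 180 days, which is hard to credit. The general pattern stands: the bias in a count test fades as events become frequent.

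**5. If some subjects qualify only through the index episode.** At p = 50%, k = 1 (mean 1 event), the false-reduction rate falls from 80% to 60%, 34%, 12% and 2.5% as that share rises from 0 to 25%, 50%, 75% and 100%. At a mean of 0.357 with k = 1, a 50% share still leaves 92%.

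**6. If risk rises after discharge.** A 1.25-fold rise (assumed) cuts about 96% to 48% at p = 30%, k = 0.5, and 80% to 11% at p = 50%, k = 1. It leaves about 97% at p = 30%, k = 1. At p = 50%, k = 1, a 1.5-fold rise removes the false reductions and gives false increases in 20% of trials.

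**The case against.** **The index episode may satisfy inclusion 7.** Screening can begin on the first day of hospitalization (9.1.2) or immediately after hospitalization (9.1), so the index admission or its ED visit could literally fall before screening. The *or* in 9.1.2 against the *and* in Table 3 leaves this unsettled. A reader might infer that the floor survives removal of the index admission for every subject. The documents do not establish that. A separate event is the more natural reading, because item 4 would otherwise leave item 7 empty, but it is not stated.

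**The index admission already floors the composite.** True as the plan is written. The entry-rule problem becomes decisive once the index admission is removed, which is the obvious first repair.

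**The rate and the equal-risk assumption are mine.** This stands. The plan's 30% is a hospitalization rate from other studies, and adding ED visits can only raise it. Section 7 says relapse risk is substantially increased after an acute admission, without a figure. That pushes the other way, but it leaves the result a mixture of entry rule, drift and drug effect in unknown proportions.

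**As a yes/no rate the test could never show harm.** A reader might infer this, since the pre value would be 100% and every discordant pair would favour the drug. But 9.7.1.9 treats the outcomes as continuous and specifies ANCOVA; no paired test of proportions is planned for this endpoint.

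**Secondary p-values are labelled hypothesis-generating.** Section 9.7.1.9 gives multiplicity as the reason. The label lowers the stakes but does not correct a biased estimate.

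**Conclusion.** The concern holds in conditional form. As written, with the index admission counted, the 180-day pre-switch composite is at least 1 for every subject and the post-switch composite is not, so the planned time effect can be significant with an inactive drug. With the index admission removed, the bias remains for subjects who met inclusion 7 through another event and vanishes only if the index episode qualified everyone.

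With a separate event for all, equal underlying rates before and after, and N = 90, false reductions run at about 67-100%, 12-100% and 4-91% for source rates of 30%, 50% and 70%. These rest on assumed composite rates and gamma-Poisson counts. It would go too far to say that a false positive is certain, or that its rate must be far above 5%: frequent events or raised post-discharge risk could shrink or reverse it.

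This concerns one window of one secondary endpoint. Section 9.7 states that no formal analysis was performed, so it is a flaw in the plan and not in a reported result. It should be corrected in any reuse of the design.

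**What to change.** In 9.7.1.9, for the 180-day ED-plus-hospitalization composite:

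1. Exclude the index episode (the admission and its ED visit) from the pre-period count. Reconcile 9.1.2 with Table 3, footnote f, state whether the index episode could satisfy inclusion 7, and record for each subject whether another event met it. The record must show whether a non-index event was needed for entry, not merely whether one existed.
2. Replace the repeated-measures ANCOVA with a pre/post count model (gamma-Poisson, shared subject effect) whose likelihood conditions on the entry rule. Truncate the pre count at 1 or more only for subjects who had to qualify through a non-index event; truncating everyone would not allow a pre count of 0 in those who qualified through the index episode.
3. If a yes/no rate is reported, give the post-switch proportion with a 95% CI and no pre/post test.
4. As a sensitivity analysis only, compare with days −360 to −181 from the same Medicaid and Department of Mental Health sources.
5. State that a pre/post reduction in this endpoint cannot by itself be attributed to the drug.

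**Cost:** SAP wording, one extra field per subject, a few lines of model code and a longer look-back in a search already planned.

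**Downsides:** the model depends on its gamma-Poisson form and gives a wider interval. A version truncating all subjects rejected 2.5-8.5% of the time under no effect (200 replicates per case), but only on data from its own family; the mixed truncation above has not been checked. The earlier window may include long-acting injectable treatment, incarceration or no oral treatment, because those eligibility look-backs reach only 6 to 7 months (9.3.1 item 8; 9.3.2 items 2 and 9).
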